10.2.5 Shipping of Specimen(s)

Flash frozen tumor for extraction of RNA and DNA and for protein extraction:

[name], Sarcoma Biology Lab
Human Oncology and Pathogenesis Program
Memorial Sloan-Kettering Cancer Center
Zuckerman Research Building
Attn: [name] [name]
[name]
New York, NY 10065
Lab [contact]
Lab [contact]
Email: [contact]

Fresh tumor fixed in formalin:
[name].
Memorial Sloan-Kettering Cancer Center
Department of Pathology
[name]
New York, NY 10065-6007
[contact]
Email: [contact]

Plasma for imatinib levels and Plasma for BGJ398 will be shipped to MSK. MSK will batch ship the samples to WuXi AppTec Co. Ltd.

All participating sites will notify the Multicenter Trial Research Staff at MSKCC (Email: [contact]) when samples are shipped by completing and emailing the sample requisition form.

Correlative studies will be performed on all obtained biopsy specimens detailed as the following.

1. Molecular based correlative studies

1a. Phenotypic characterizations by immunohistochemistry (IHC)

For pathway response studies, we will assess the baseline characteristics of the MAP kinase, FGF, and KIT pathway members in FFPE samples collected from all patients. Previous studies have demonstrated the reliability of pathway members KIT, pKIT, pERK1/2, pAKT, PTEN, p-S6, p4E-BP1, pFRS2, FRS2, pPRAS40, pSTAT3, and STAT3, which will be evaluated by IHC. Baseline tissue characteristics will be derived from histological characterization for KIT, CD34 and DOG1. FGF2 and FGFR will also be screened by IHC on all tumor samples.

MEMORIAL SLOAN-KETTERING CANCER CENTER
IRB PROTOCOL

IRB#: 14-140 A (7)

1b. Genetic characterization of tumors

All tumor specimens will be genotyped via standard sequenom assay for hotspot mutations in KIT, PDGFRA and BRAF that are commonly mutated in GIST. In addition, we will perform multiplex custom exome capture coupled with deep-sequencing for genes that are frequently implicated in GIST pathogenesis, including KIT, PDGFRA, BRAF, NF1, ETV1, PTEN, NRAS, HRAS, KRAS and p53 mutational status.

1c. Transcriptome characterization of tumors

As an exploratory study, we will perform custom transcriptome analysis of a custom ETV1-dependent gene signature in GIST[25] in FFPE samples from all patients using nanostring, because ETV1 protein level is very unstable.

1d. Pharmacodynamic studies by IHC, WB and immunofluorescence

FFPE tumor tissue and pre-and post-treatment tumor frozen samples from the first 20 patients will be evaluated for inhibition of ETV1 and target pathway inhibition (MAP kinase, FGF, and KIT pathways). A variety of pathway markers of the MAP kinase and KIT pathways, including KIT, pKIT, pERK1/2, pAKT, PTEN, p-S6, p4E-BP1, pFRS2, FRS2, pPRAS40, pSTAT3 and STAT3 will be evaluated by IHC. ETV1 protein levels will also be evaluated by both western blot and immunofluorescence of frozen tissues, since there is no IHC grade ETV1 antibody.

1e. Pharmacodynamic studies by transcriptome

We will perform custom transcriptome analyses of the ETV1-dependent gene signature in GIST in pre- and post-treatment biopsies to assess the inhibition of the ETV1 transcriptional activity and correlate with response.

1f. Phenotypic changes in pre- and post-treatment tumors by IHC

In addition to the IHC of pKIT, pAKT, pERK1/2, etc as outlined in 1d in pre- and post-treatment biopsies, we will explore the relationship between the immunostains with the effects on tumor growth as assayed by the proliferation marker, Ki-67, and the apoptosis/cell death marker, cleaved caspase 3.

1g. Steady state plasma imatinib trough levels

The acute and steady state imatinib level will be assessed in all Phase Ib patients (one sample/timepoint). Patients enrolled onto treatment schedule A will have a plasma sample for imatinib levels drawn at C1D2 and C1D21 before imatinib is dosed on those days. Patients enrolled onto treatment schedule B will have a plasma sample for imatinib level drawn at C1D2, C1D7 and C1D21 before imatinib is dose on those days. The steady state imatinib trough levels will be obtained and evaluated in the two-week imatinib lead in phase (one sample/patient) and in the combination therapy phase (one sample/patient) from all patients in the Phase II portion of the trial. We will evaluate the effects of BGJ398 on imatinib steady state trough levels by comparing these two phases.

1i. BGJ398 pharmacokinetic assessment

BGJ398 levels will be assessed in all Phase Ib patients (1 sample per timepoint). Patients enrolled onto treatment schedule A will have plasma samples for BGJ398 levels collected at

MEMORIAL SLOAN-KETTERING CANCER CENTER
IRB PROTOCOL

IRB#: 14-140 A (7)

C1D1 at 0, 1, 2, 4, 6, 8 hours; C1D2 24 hr time point; and C1D21 at 0, 1, 2, 4, 6, 8 hours. Patients enrolled onto treatment schedule B will have plasma samples for BGJ398 levels collected at C1D1 at 0, 1, 2, 4, 6, 8 hours; C1D2 24 hr time point after the first dose of BGJ398&imatinib; C1D7 at 0, 1, 2, 4, 6, 8 hours; C1D15 at 0 hours and C1D21 at 0 hours.

1i. FGF2 serum/plasma levels by ELISA

A commercially available ELISA kit for serum/plasma FGF2 (Bioagilytix) will be evaluated in all patients at baseline, with the initiation of imatinib, after imatinib lead in and serially, after the initiation of combination therapy. FGF2 levels will be correlated to primary and secondary outcomes.

2. **Sample collections pre- and during treatment**

- 2a. Archival biopsy FFPE samples (as available, ~25 unstained FFPE sections of standard 5 µm slides, OR 10-20 unstained FFPE sections of 10 µm slides)
- 2b. Frozen pre-treatment core biopsy samples (up to five cores)
- 2c. Frozen 1 week post-combination treatment biopsy samples (up to five cores)
- 2d. Frozen post-treatment biopsy or surgical samples at disease progression (if possible)
- 2e. Whole blood for research purposes. These samples will possibly be used for serum FGF2 levels and screening for other potential soluble protein biomarkers, etc. pre-treatment and 1 or 2 weeks after treatment and periodically, day 1 of each cycle.

3. **Imaging based correlative studies:**

FDG PET per standard of care will be obtained pre-treatment and three weeks (C1D21) after initiation of the combined imatinib and BGJ398 treatment in the Phase II portion. These images will be evaluated to determine whether the FDG PET studies can be used to determine and predict treatment response.

4. **Imatinib Levels:**

As imatinib is standard of care for patients with untreated inoperable locally advanced or metastatic GIST, imatinib levels will be tested to ensure that BGJ398 does not affect imatinib serum levels. In Phase Ib, imatinib levels will be tested on C1D2 (24 hour timepoint after the first dose of imatinib&BGJ398) and C1D21 (prior to dosing on that day) on both treatment schedules (A and B). In phase Ib, on schedule B, imatinib level will also be tested on C1D7 (prior to dosing on that day). All participants on the Phase II portion will undergo a 2-week lead in of single agent imatinib in order to establish a steady-state serum imatinib trough level. Imatinib levels will be rechecked during week 3 and week 5 of the combination therapy. We will correlate imatinib levels to primary and secondary outcome measures. Imatinib levels will be stratified into quartiles as done previously [31].

5. **FGF2 Serum Levels:**

Preclinical data suggests that FGF2 levels may correlate with the development of imatinib resistance and may predict response to inhibition with BGJ398. Blood will be collected at baseline (if not on imatinib), after the imatinib lead-in, and during week 3 and 5 of the combination therapy. We will correlate FGF2 levels to our primary and secondary endpoints with the hope of establishing an integral biomarker for BGJ398 and evaluating the penetrance of the FGF pathway in GIST. If collected blood specimen is only adequate for 1 assay, imatinib levels should be prioritized.

Please reference the laboratory manual for instructions on sample labeling and shipping.

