3.3.3 Pharmacokinetics of Imatinib mesylate

3.3.3.1 Pharmacokinetics of Imatinib in healthy subjects and patients with normal hepatic and renal function

The pharmacokinetics of Gleevec® have been evaluated in healthy subjects and in population pharmacokinetic studies in over 900 patients. Imatinib is well absorbed after oral administration with C_{max} achieved within 2-4 hours post-dose. Mean absolute bioavailability is 98%. Following oral administration in healthy volunteers, the elimination half-lives of imatinib and its major metabolite, the N-desmethyl derivative, were approximately 18 and 40 hours, respectively. Mean imatinib AUC increased proportionally with increasing dose in the range 25mg - 1000mg. There was no significant change in the pharmacokinetics of imatinib on repeated dosing, and accumulation is 1.5-3 fold at steady state when Gleevec® is dosed once daily. At clinically relevant concentrations of imatinib, binding to plasma proteins in *in vitro* experiments is approximately 89-96%, mostly to albumin.

A pharmacokinetic study following continuous once daily oral administration of imatinib has been performed in two GIST patients. The preliminary results showed that the PK profiles in GIST patients are similar to that observed in CML patients. Imatinib is rapidly absorbed and a C_{max} of 2.9 µg/ml was reached at steady state following a 400 mg daily dose. The terminal life was 13h and there was 1/5 fold drug accumulation after one month dosing. The AUC (0-24) values were 23,748 ng/h/ml at steady state after a 400 mg dosing, which is similar to those seen in CML patients.

The terminal half-life ($t_{1/2}$) averaged to 10 to 23 hours (18 hours for the parent and 40 hours for the major metabolite (see below)) and there was a 2-3 fold accumulation of drug at steady state. These data are compatible with a schedule of once daily administration. The increase in mean plasma AUC values was proportional to dose up to 750 mg/day. The mean plasma AUC (0-24) at steady state following a continuous once daily oral dose of 750 mg was 62,259 ng/h/ml.

A food effect study has shown no significant differences in absorption when imatinib was administered either with food or in the fasting state. Since this agent has potential to irritate gastric mucosa, it is therefore strongly recommended that the agent be taken with food to decrease risk of gastric irritation.

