6.2 Subject Exclusion Criteria

Patients meeting any of the following criteria are excluded from the study:

Exclusion criteria:

- For phase I, prior intolerance to imatinib at a dose of 400 mg daily.
- For phase II, any receipt of cytotoxic, biologic, or immune therapy aimed to treat GIST except for adjuvant imatinib systemic therapy that concluded at least 90 days prior to registration. For Phase I, patients are eligible regardless of prior therapy.
- Chronic liver disease (e.g., cirrhosis)
- Known positive serology for HIV, active Hepatitis B, and/or active Hepatitis C infection.
- Patients have a history or current evidence of Central Serous Retinopathy (CSR) or retinal vein occlusion (RVO) or major predisposing factors to CSR or RVO (e.g. uncontrolled glaucoma or ocular hypertension) in the opinion of the study ophthalmologist.
- History of retinal degenerative disease
- Active corneal disorder or keratopathy (e.g. corneal abrasion, bullous keratopathy)
- Severe and/or uncontrolled medical disease, including:
 - Uncontrolled diabetes mellitus (A1c > 8)
 - Chronic Kidney Disease Stage III or higher (Creatinine Clearance $< 60\text{mL}/\text{min}/\text{m}^2$ by Modified Diet in Renal Disease (MDRD) calculation)
 - Active, uncontrolled infection
- Known active brain metastasis unless they have been treated and shown documented radiographic stability for 28 days.
- Known other active malignancy (other than malignancies which the investigator determines are unlikely to interfere with treatment and safety analysis).
- Patients have clinically significant cardiovascular disease, including any of the following

MEMORIAL SLOAN-KETTERING CANCER CENTER IRB PROTOCOL

IRB#: 14-140 A (7)

- Any history of acute coronary syndrome including myocardial infarction, stable or unstable angina, CABG, coronary angioplasty or stenting, or known obstructive coronary artery disease
- Symptomatic chronic heart failure (New York Heart Association Criteria, Class II-IV)
- Evidence of clinically significant cardiac arrhythmias and/or conduction abnormalities < 6 months prior to screening except atrial fibrillation (AF) and paroxysmal supraventricular tachycardia (PSVT)
- Any history of thrombotic cerebrovascular accident or other arterial thrombosis
- Uncontrolled arterial hypertension (systolic blood pressure >155 mmHg or diastolic >95 mmHg) despite appropriate medical therapy.

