9.0 TREATMENT/INTERVENTION PLAN

Treatment will be administered on an outpatient basis. Reported adverse events and potential risks are described in Section 11. Appropriate dose modifications of imatinib and BGJ398 are described in section 9.2. No investigational or commercial agents or therapies other than those described below may be administered with the intent to treat the patient's malignancy.

MEMORIAL SLOAN-KETTERING CANCER CENTER IRB PROTOCOL

IRB#: 14-140 A (7)

Imatinib will be self administered orally by the patient on a daily basis throughout the treatment cycle. The standard treatment dose is 400 mg PO QD. 400 mg capsule will be used unless otherwise specified by the treating physician. BGJ398 will be taken at the RP2D and treatment schedule chosen from the Phase Ib portion of the trial. The RP2D selected may be lower than the MTD based on PK data and clinical tolerance beyond Cycle 1. BGJ398 is taken daily for a duration determined by the treatment schedule appropriate for the given dose level. In the event of dose delays of BGJ398, Day 1 of the following cycle will be defined as the day that BGJ398 is restarted. A pill diary for both medications will be provided and recorded (Appendix B). This will be used to assure compliance with the regimen.

On the Phase Ib portion, the timing of pharmacokinetic sample collections will be dependent on the treatment schedule onto which that patient is enrolled. For treatment schedule A pharmacokinetic samples will be drawn on Cycle 1, Day 1 at the following timepoints: 0, 1, 2, 4, 6, 8, and 24 hrs; and Cycle 1, Day 21 at the following timepoints: 0, 1, 2, 4, 6, and 8 hours. For treatment schedule B pharmacokinetic samples will be drawn on Cycle 1, Day 1 at the following timepoints: 0, 1, 2, 4, 6, 8, and 24 hrs; Cycle 1, Day 7 at the following timepoints: : 0, 1, 2, 4, 6, and 8 hours, Cycle 1, Day 15 at timepoint 0hr and Cycle 1, Day 21 at timepoint 0hr.

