
**MEMORIAL SLOAN-KETTERING CANCER CENTER
IRB PROTOCOL**

IRB#: 14-140 A (7)

	
window for C1D15 and C1D21 timepoint. Other levels may be drawn as clinically indicated.
 
i: For treatment schedule A plasma for imatinib levels will be drawn concurrently with BGJ398 levels at the following two time points: C1D2 (24 hours post-first dose) and C1D21. Both time points will be drawn before dosing imatinib on that day. C1D2 must be done on the exact date, and C1D21 may be drawn within a -3/+1 day window. Other levels may be drawn as clinically indicated.
 
For treatment schedule B plasma for imatinib levels will be drawn concurrently with BGJ398 levels at the following three timepoints: C1D2 (24 hours post-first dose), C1D7 and C1D21. All time points will be drawn before dosing imatinib on that day. C1D2 must be done on the exact date. C1D7 can be drawn within a -2/0 day window and C1D21 can be drawn within a -3/+1 day window. Other levels may be drawn as clinically indicated.
 
j. CBC and Blood Chemistry performed on Day 1 of each cycle must be resulted prior to treatment.
 
All assessments are to be done +/-3 days of the scheduled timepoints unless otherwise noted above. Radiologic assessments (CT, PET, TTE) are to be done +/-7 days from the scheduled appointment.

--	--

Table 10.A: Pharmacokinetic Assessments of BGJ398 on Treatment Schedule A

Treatment Cycle	Day	PK Sample # BGJ398 (Plasma)	Time Relative to Dose
1	1	1	Pre-dose ^a
1	1	2	1hr ± 5 min
1	1	3	2hr ± 5 min
1	1	4	4hr ± 10 min
1	1	5	6hr ± 10 min
1	1	6	8hr ± 15 min
1	2	7	24hr ± 60 min ^a
1	21	8	Pre-dose ^a
1	21	9	1hr ± 5 min
1	21	10	2hr ± 5 min
1	21	11	4hr ± 10 min

**MEMORIAL SLOAN-KETTERING CANCER CENTER
IRB PROTOCOL**

IRB#: 14-140 A (7)

			min
1	21	12	6hr ± 10 min
1	21	13	8hr ± 15 min
Any	Any	101, 102, etc	As clinically indicated

a: These levels should be drawn just prior to administration of BGJ398 plus imatinib on that day

Note: C1D21 will have a -3 days/+1 day window, this window differs from all other PK visits

Table 10.B: Pharmacokinetic Assessments of BGJ398 on Treatment Schedule B

Treatment Cycle	Day	PK Sample # BGJ398 (Plasma)	Time Relative to Dose
1	1	1	Pre-dose ^a
1	1	2	1hr ± 5 min
1	1	3	2hr ± 5 min
1	1	4	4hr ± 10 min
1	1	5	6hr ± 10 min
1	1	6	8hr ± 15 min
1	2	7	24hr ± 60 min ^a
1	7	8	Pre-dose ^a
1	7	9	1hr ± 5 min
1	7	10	2hr ± 5 min
1	7	11	4hr ± 10 min

**MEMORIAL SLOAN-KETTERING CANCER CENTER
IRB PROTOCOL**

IRB#: 14-140 A (7)

1	7	12	6hr ± 10 min

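### On Schedule A, the phase Ib imatinib levels cannot separate a BGJ398 effect from ordinary accumulation; assaying the C1D1 pre-dose sample would largely close the gap at low cost

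*Combined protocol and SAP*

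**What the plan says.** Section 2 lists the pharmacokinetics of both BGJ398 and imatinib as a phase Ib secondary objective. Section 10.2.5, item 4 (Imatinib Levels) gives the reason for measuring imatinib: "imatinib levels will be tested to ensure that BGJ398 does not affect imatinib serum levels". The phase Ib draws follow directly: "In Phase Ib, imatinib levels will be tested on C1D2 (24 hour timepoint after the first dose of imatinib&BGJ398) and C1D21". One more draw is then added: "on schedule B, imatinib level will also be tested on C1D7 (prior to dosing on that day".

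Footnote i to Table 9 (Section 10.1.1) confirms the Schedule A plan: "C1D2 (24 hours post-first dose) and C1D21. Both time points will be drawn before dosing imatinib on that day". Under Section 5.2.3, BGJ398 is taken on days 1-21 on Schedule A and on days 1-7 on Schedule B.

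Phase Ib patients have progressed on imatinib but may enter at any phase of treatment (Section 4.1), and Section 6.2 adds: "For Phase I, patients are eligible regardless of prior therapy". No lead-in or washout is stated for phase Ib. Phase II has a two-week imatinib-alone lead-in, and Section 10.2.5, item 1g assigns the comparison of imatinib troughs without and with BGJ398 to phase II. For phase Ib, Section 14 names only BGJ398 pharmacokinetic parameters and gives no analysis of imatinib levels.

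**The concern.** To see whether BGJ398 changes imatinib exposure, one needs an imatinib level without BGJ398, or a pair of levels between which only BGJ398 exposure differs. Schedule A has neither. Its first imatinib level comes 24 hours after the first combined dose and its second while BGJ398 is still being taken.

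The first level also means different things in different patients. In someone continuing imatinib it is close to a steady-state trough; in someone restarting it is the trough after a single dose. A rise to C1D21 may then be accumulation, interaction or both.

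An interaction is plausible on the protocol's own account. Section 3.2.2.1 describes BGJ398 as a potent reversible CYP3A4 inhibitor, and Section 3.3.3.1 names CYP3A4 as the main enzyme for imatinib. At stake is whether the phase Ib imatinib data can say anything on this before the phase II dose and schedule are fixed.

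**Working it through.** **Inputs.** From Section 3.3.3.1: parent half-life about 18 h, range 10-23 h, 13 h in two GIST patients, and "accumulation is 1.5-3 fold at steady state" with once-daily dosing. Dosing interval: 24 h. Draw days and windows come from Table 9 and its footnotes.

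**Assumptions.** One compartment, dose-proportional, unchanged 400 mg daily, no missed doses.

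**Step 1: the protocol's accumulation figure.** With q = 2^(-24/t½), accumulation is R = 1/(1 - q).

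| t½ (h) | q | R |
|---|---|---|
| 10 | 0.19 | 1.23 |
| 13 | 0.28 | 1.39 |
| 18 | 0.40 | 1.66 |
| 23 | 0.49 | 1.94 |

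The 18 h half-life gives a value inside the stated 1.5-3. R = 1.5 needs about 15 h and R = 3 about 41 h, so the upper end does not follow from the stated parent half-lives. Both ranges are carried forward.

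**Step 2: Schedule A, no interaction.** The trough after n doses relative to the trough after one dose is (1 - q^n)/(1 - q). C1D2 follows one dose and C1D21 follows 20.
- Continuing 400 mg at steady state: C1D21/C1D2 is about 1.0.
- Restarting: 1.23 (10 h) to 1.94 (23 h), or 1.5-3 on the protocol's figure.
- Mixed group with share f restarting: the geometric mean ratio is R^f. With f = 0.5 (assumed) and R from 1.5 to 3, it is 1.22 to 1.73.

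Suppose a true interaction of 1.5-fold (assumed) that appears only after C1D2. A continuing patient would show about 1.5, the same as a restarting patient with no interaction and R = 1.5. Without a baseline and a record of prior imatinib, the two cannot be told apart.

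**Step 3: an opposite distortion.** Section 3.1.1 names 800 mg daily as one option after progression on 400 mg. If a patient entered from steady state on 800 mg (assumed), the no-interaction C1D21/C1D2 ratio on 400 mg would be 1/(1 + q): 0.84 at 10 h, 0.72 at 18 h, 0.67 at 23 h. At 18 h, the same 1.5-fold interaction would read 0.716 x 1.5 = 1.07.

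**Step 4: Schedule B.** C1D7 is on BGJ398; C1D21 is 21 - 7 = 14 days after its last dose. In a restarting patient with no interaction, C1D21/C1D7 = (1 - q^20)/(1 - q^6): 1.004 at 18 h and 1.013 at 23 h. At the window extremes (day 18 against day 5) it is 1.025 and 1.059. Accumulation is thus nearly complete by C1D7, and a clear fall from C1D7 to C1D21 would point to an inhibitory interaction. With a half-life of 40 h, close to what 3-fold accumulation implies, the ratio would be 1.09, or 1.23 at the window extremes. Residual accumulation pushes the ratio up, so it could mask a fall but not create one.

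**The case against.** The strongest reply is that phase Ib was never meant to settle this question. The purpose sentence in item 4 is framed around untreated patients, who are the phase II population. Phase II has the imatinib-alone lead-in, and item 1g places the comparison there. In phase Ib the levels are simply to be assessed. That stands and lowers the importance of the point. It does not remove it: the phase Ib draws are listed under that purpose, Section 2 makes imatinib pharmacokinetics a phase Ib objective, and the phase II comparison comes only after the RP2D and schedule are chosen. The phase II plan also needs tidying: Section 14 describes the contrast as before and after the lead-in, with two samples per phase, whereas item 1g compares lead-in with combination, with one sample each.

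A reader might infer three stronger things that the documents do not support.
- *That all of phase Ib rests on C1D2 and C1D21.* Schedule B adds C1D7, and Step 4 shows that this pair is informative. Schedule B is optional, however, so phase Ib could run entirely on Schedule A.
- *That the plan will interpret a C1D21/C1D2 ratio.* No such ratio, and no phase Ib interaction test, is planned.
- *That the RP2D will be distorted.* Section 9.0 says: "The RP2D selected may be lower than the MTD based on PK data and clinical tolerance beyond Cycle 1". It does not say that imatinib levels are part of those data. Section 14 names only BGJ398 parameters for phase Ib, and says the phase II imatinib analysis will not change the dose given.

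It is also fair that the remedy helps only patients already at steady state on 400 mg at C1D1. The documents do not say how many there will be, and phase Ib may enrol as few as 6.

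**Conclusion.** The point holds as a low-cost improvement, mainly for Schedule A. As sampled, Schedule A imatinib levels cannot show whether BGJ398 affects imatinib. With no interaction, C1D21 relative to C1D2 could be anywhere from about 1 (continuing 400 mg) to 1.2-1.9 (restarting, half-life 10-23 h) or 1.5-3 (restarting, protocol figure).

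This rests on simple one-compartment accumulation and on imatinib status at C1D1 being open, which the eligibility text leaves it. The share of patients restarting is unknown; the one-half used above is only illustrative. The Schedule B reading assumes that BGJ398's effect has worn off by C1D21. The documents give no BGJ398 half-life, but BGJ398 levels at C1D15 and C1D21 can help check this.

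It would be wrong to conclude that the trial as a whole cannot address the interaction, or that dose selection is compromised.

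**What to change.** 1. Add an imatinib assay to the C1D1 pre-dose plasma already drawn as PK sample 1 (Tables 10.A and 10.B). Amend the lab manual (Appendix I) to match, since it supplies the extra aliquot tube only at the current imatinib time points.
2. Record on the CRF the dose and date of the last prior imatinib, and how long that dose had been taken.
3. Add a short paragraph to Section 14:
   - Schedule A: report the within-patient log ratio of the C1D21 trough to the C1D1 trough in patients already at steady state on 400 mg at C1D1. Report the others descriptively, with no interaction statement.
   - Schedule B: report C1D7/C1D1 in the same kind of subset, and C1D7 (on BGJ398) against C1D21 (14 days off) in all patients. State the expected no-interaction C1D21/C1D7 ratio of about 1.00-1.06 in restarting patients (half-life 18-23 h), and show the BGJ398 levels at C1D15 and C1D21 beside it.

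Cost: at most about 30 extra assays (the phase Ib maximum), one aliquot tube per patient, one CRF entry and one paragraph. No dose, visit or blood draw changes. The downside is that the baseline-based estimate rests on a subset that may be small, so it should be reported with its interval and number of patients and treated as descriptive.
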